2 PROTOCOL REVISIONS

Amendment Number	Approval Date	Modification
Amendment #1	06SEP2018	Reflects a change in study staff. No modifications to the protocol or consent form.
Amendment #2	05OCT2018	Congruency review for NIH grants. No modifications to the protocol or consent form.
Amendment #3	18DEC2018	Created protocol v1.1 dated 28NOV2018 
 • ALCMI's biorepository location modified • ALCMI's data repository vendor modified • Remote informed consent form process modifications • Minor modifications to the subject's experience • Informed consent form modifications
Amendment #4	20DEC2018	Study opened to enrollment; funding resolved. No modifications to the protocol. Consent form modified to reflect date study open to enrollment.
Amendment #5	19FEB2019	Minor modifications to the Blood Collection & Handling Instructions. No modifications to the protocol or consent form.
Amendment #6	19FEB2019	Created protocol v1.2 dated 13FEB2019. 
 • Reflects Administrative Clarification 1.02112019 – change from QConsent to OpenMedNet online consent platform.
Amendment #7	18MAR2019	Modifications to consent form. No modifications to the protocol.
Amendment #8	25APR2019	Created protocol v1.3 dated 18MAR2019. 
 • Administrative Clarification 2.03072019 – nurse hotline.
Amendment #9	15MAY2019	Administrative Clarification 3.04292019 – inclusion criteria clarification. No modifications to protocol or consent form.
Amendment #10	26SEP2019	Marketing material – Webpage video
Amendment #11	02NOV2019	Created protocol v1.4 dated 12SEP2019 
 • Protocol modified to reflect all prior amendments • Protocol Revisions section added • Follow-Up language modified • Archival tissue collection added • Document formatting corrected
Amendment #12	03AUG2020	Created protocol v1.5 dated 19JUN2020 
 • Change of PI • Administrative Clarification v1.06192020 acknowledging change of PI
Amendment #13	26JAN2021	Created protocol v1.6 dated 21JAN2021 
 • Modified online consent platform language as result of vendor change from OpenMedNet to RedCap • Modified hotline language given change in personnel • Modified language to allow for remote monitoring visits
Amendment #14	Pending	Created protocol v1.7 dated 03FEB2021 
 • Modified schematic to match follow-up language which was approved in Protocol v1.4 dated 12 SEP2019 (Section 10.11, Study Calendar) • Added visit windows to each follow-up visit (Section 10.11, Study Calendar)

Title: Study of Plasma Next Generation Sequencing for Remote Assessment, Characterization, Evaluation of Patients With ALK Drug Resistance (SPACEWALK)

3 DEFINITIONS

Investigator: Individual responsible for the study at the site.
 Site: Tertiary center where study is performed by the Investigator.
 Study Manager: Qualified and trained collaborator acting as the point of contact.

Abbreviation	Definition
ALCF	Addario Lung Cancer Foundation
ALCFMI	Addario Lung Cancer Medicine Institute
ALK	Anaplastic Lymphoma Kinase
cfDNA	Circulating cell-free deoxyribonucleic acid
CFR	Code of Federal Regulations
CLIA	Clinical Laboratory Improvement Amendments
CNS	Central nervous system
CRF	Case Report Form
ctDNA	Circulating tumor deoxyribonucleic acid
CTMS	Clinical trials management system
DF/HCC	Dana-Farber/Harvard Cancer Center
DNA	Deoxyribonucleic acid
DSMP	Data Safety Monitoring Plan
EGFR	Epidermal growth factor receptor
FDA	US Food and Drug Administration
GCP	Good Clinical Practice
GLP	Good Laboratory Practice
GoYLC	Genomics of Young Lung Cancer study
HIPAA	Health Insurance Portability and Accountability Act
INHERIT	Investigating Hereditary Risk from T790M study
IRB	Institutional Review Board
m	Month
MCA	Master Collaboration Agreement
NGS	Next generation sequencing
NIH	National Institutes of Health
NSCLC	Non-small cell lung cancer
OS	Overall survival
PFS	Progression-free survival
PHI	Protected Health Information
PI	Principal Investigator
RR	Response rates
SLB	Scientific Leadership Board
SOP	Standard Operating Procedures
TKI	Tyrosine-kinase inhibitor
TTD	Time to treatment discontinuation
US	United States

Title: Study of Plasma Next Generation Sequencing for Remote Assessment, Characterization, Evaluation of Patients With ALK Drug Resistance (SPACEWALK)

4 ABSTRACT

Patients with advanced anaplastic lymphoma kinase (ALK) positive non-small cell lung cancer (NSCLC) gain tremendous benefit from treatment with ALK-targeted tyrosine kinase inhibitors (TKI)¹. Crizotinib, the first ALK TKI entering the clinic, has remained a standard of care for the last six years. Resistant mechanisms arising after crizotinib failure include secondary ALK resistance mutations, activation of bypass track pathways and drug-specific pharmacodynamic issues such as low blood brain barrier penetration.

More potent next generation ALK TKIs such as ceritinib, alectinib, brigatinib and lorlatinib are under development, with some currently commercially available in parts of the world. With the expected median overall survival (OS) for metastatic ALK positive lung cancer patients now over two years and the expected widespread availability of several new ALK TKIs, most of those patients will receive multiple lines of different ALK inhibitors. When given after progression on crizotinib, those next generation agents yield response rates (RR) of 40-60% and progression free survival (PFS) times around 6-10 months(m)^{2,3}. But little is known about the resistance mechanisms arising after failure to a next generation ALK TKI or about crossed resistance between different next generation ALK TKIs.

The largest study to date addressing ALK TKI resistance mechanisms was a single-center study of tumor specimens from 83 patients, but only 48 of them had resistance after treatment with a next generation ALK TKI⁴. This study found that ALK resistance mutations were more common after progression on next generation ALK TKIs than after progression on crizotinib (56% vs 20%, respectively). A wide range of different ALK resistance mutations was identified and while numbers were small, results suggested a link between different ALK TKIs and specific resistance mutations. Furthermore, this and other emerging data also indicates that drug resistance mediated by some secondary ALK mutations can be overcome by using specific alternate ALK targeted therapies⁵.

[figure not shown]
Tumor genotyping is now used in lung cancer patients with advanced disease and adenocarcinoma histology to decide the best first-line treatment. For those lung cancer patients whose tumor harbor an EGFR mutation or an ALK rearrangement treatment with specific TKIs is the best treatment option. Additionally, further tumor genotyping after tumor resistance has also demonstrated to improve outcomes in TKI-resistant EGFR-mutant NSCLC patients. The secondary EGFR T790M mutation accounts for resistance in 50% of the patients with EGFR-mutant lung cancer and tumor progression while on a first-generation EGFR TKI⁶. In those T790M positive patients, continuing EGFR inhibition with osimertinib, a third-generation EGFR TKI, has demonstrated to be superior to chemotherapy⁷. Until recently sequential tumor genotyping required patients to undergo new invasive procedures. With the availability of plasma-based genotyping technologies it is now feasible to characterize tumor genomics in cancer patients by analyzing the tumor DNA present in patients' blood⁸. Circulating tumor DNA found among patients' circulating free DNA (cfDNA) is shed into the bloodstream from lysed tumor cells. In EGFR-mutant NSCLC patients and resistance to first-generation EGFR TKI the detection of the secondary EGFR T790M mutation using a plasma-based assay has demonstrated to be as effective as genotyping from tumor specimens⁷. Additionally, some plasma-based next-generation sequencing (NGS) platforms are now able to test a range of tumor mutations within a single analysis. These NGS assays are technically validated and clinically available, but are often not being studied in a systematic way.

Title: Study of Plasma Next Generation Sequencing for Remote Assessment, Characterization, Evaluation of Patients With ALK Drug Resistance (SPACEWALK)

In the present study, we plan to investigate resistance mechanisms arising in ALK-positive NSCLC patients after progression while on a next generation ALK TKI using a plasma-based NGS platform. We will monitor the next treatment line received by those patients to assess the benefit derived from immediate access to subsequent lines of therapy based on the specific genomic profile identified by baseline plasma NGS. We plan to use a commercially available, CLIA certified, plasma NGS platform to offer noninvasive testing of the cfDNA to characterize the resistant tumor profile. Plasma NGS results will be returned to subjects and their provider to inform of the tumor genomics and possible sensitivities of any detected resistance mutations to available ALK TKIs.

Because it is now possible for patients to send plasma samples directly to central laboratories for NGS analysis, we will leverage a remote consent and participation approach to open enrollment to all nationwide patients with metastatic ALK-positive NSCLC. Our overarching hypothesis is that we can conduct a remote consent study using plasma NGS to characterize ALK resistance mechanisms arising at progression to a next-generation ALK TKIs, and predict the chance of response to different ALK TKIs according to the plasma NGS results.

4.1 STUDY SCHEMA

5 BACKGROUND & RATIONALE

5.1 ALK TKIS

ALK-rearrangements are the second most common targetable genotype among patients with non-small cell lung cancer. Patients with advanced ALK-positive NSCLC gain tremendous benefit from treatment with ALK TKI's¹. Crizotinib, the first ALK TKI entering the clinic, has remained as the preferred first line treatment option for the last six years. When compared with a standard first line platinum-based chemotherapy, crizotinib yielded superior RR and PFS (74% vs 45% and 10.9 m vs 7.0 m, respectively)⁹. New potent next-generation ALK TKIs such as ceritinib, alectinib, brigatinib or lorlatinib are under development, with some being commercially available in parts of the world. When given after progression on crizotinib, these second generation agents yield RR of 40-60% and PFS times around 6-10 m^{2,3}. In the only available Phase III trial using chemotherapy or a next generation ALK TKI (ceritinib) after progression to crizotinib and

Title: Study of Plasma Next Generation Sequencing for Remote Assessment, Characterization, Evaluation of Patients With ALK Drug Resistance (SPACEWALK)

chemotherapy, ceritinib demonstrated that maintained ALK inhibition was superior to a standard second line chemotherapy (docetaxel or pemetrexed) in overall RR (39% vs 6.9%) and PFS (5.4months vs 1.6months)¹⁰. With the average expected median OS now beyond 2 years for metastatic ALK-positive NSCLC patients, it is expected that most patients will receive several lines of therapy with different ALK TKIs.

5.2 RESISTANCE MECHANISMS TO ALK TKIs

Despite initial durable responses to ALK TKIs the emergence of drug resistance is inevitable. Some potential mechanisms of resistance to crizotinib are as follows: ALK dominant resistance, (such as secondary mutations), activation of bypass signaling pathways (including EGFR, KRAS, KIT, MET, and IGF-1R) and some crizotinib specific pharmacodynamics providing low central nervous system (CNS) exposure^{11,12,13}. The use of next generation ALK TKIs has demonstrated activity in this setting, probably due to their activity against some of the ALK resistance mutations and/or an optimal CNS exposure. But again, it is known that those patients ultimately acquire resistance to those next generation ALK inhibitors. The largest study to date addressing resistance mechanisms to new ALK TKIs was a single-center study of tumor specimens from 83 patients, but only 48 of them had resistance to a next generation ALK TKI⁴. This study found that ALK resistance mutations were more common after progression on next-generation ALK TKIs than on progression to crizotinib (56% vs 20%, respectively). A myriad of different resistant mutations was identified and while numbers were small, a link between different ALK TKIs and specific resistance mutations was suggested. Furthermore, preclinical data suggests that drug resistance mediated by some ALK resistant mutations can be overcome by using specific alternate ALK targeted therapies. Importantly, this kind of *molecularly-guided resistance therapy* is now standard in EGFR-mutant NSCLC, where osimertinib is used to overcome TKI resistance mediated by the resistant mutation *EGFR T790M*¹⁴.

5.3 PLASMA NEXT-GENERATION GENE SEQUENCING (NGS)

Biopsies are the standard method for diagnosis of cancer, allowing the histological definition and molecular characterization of the disease.¹ Nevertheless, patients often have limited tissue for molecular studies, particularly when the diagnosis is obtained from fine needle aspiration. Furthermore, the information obtained from a single biopsy provides only a limited view of a tumor, preventing an evaluation of its heterogeneity. Apoptotic or necrotic cancer cells in the tumor including metastatic sites as well as circulating tumor cells, released tumor DNA into the blood circulation as part of the total cfDNA. Therefore, in cancer patients cfDNA carries tumor-related gene abnormalities relevant for tumor development, progression, and resistance to therapy. For that reason, cfDNA in the plasma or serum could be used as a “liquid biopsy,” capable of providing the genetic landscape of all tumor lesions shedding DNA into the blood circulation. Since tumors continue to evolve during the course of the disease, acquiring new mutations that may be associated with resistance to therapy, cfDNA could be used to track for resistance mechanisms avoiding repeated invasive biopsies. Several studies have now suggested that multiplexed genotyping assays like plasma NGS can detect the mutations present in a patient’s cancer from the cfDNA present in plasma allowing the characterization of multiple tumor mutations in one single test^{15,16,17,18}. Another potential advantage of cfDNA is the monitoring of the disease. Because cfDNA is mostly of germline origin from ruptured benign cells, tumor-derived mutations are inherently present at a very low prevalence. The total amount of tumoral cfDNA present in plasma is also related to the extension of the tumor⁸, with those patients with advanced disease and systemic progression carrying a higher plasma cfDNA load.

**Title: Study of Plasma Next Generation Sequencing for Remote Assessment,
Characterization, Evaluation of Patients With ALK Drug Resistance (**SPACEWALK**)**

In lung cancer patients with acquired resistance to EGFR targeted therapies liquid biopsy for tumor genotyping has proven to be an invaluable biomarker for identifying subsets of patients with benefit from sustained alternative EGFR inhibition. Lung cancer patients harboring EGFR mutations treated with gefitinib or erlotinib and who develop a secondary *EGFR T790M* resistance mutation have been shown to benefit more from treatment with the third-generation EGFR TKI osimertinib than with chemotherapy¹⁴. In that study, *EGFR T790M* mutations identified in biopsies or in plasma rendered similar outcomes.

Overall, the plasma NGS assay from Resolution Bioscience used in the present study has demonstrated a high sensitivity and specificity, 77% and 100% respectively, when compared to other widely used plasma tests¹⁹. For the purposes of the present study sample estimation we will consider a conservative sensitivity of 70% for the NGS assay, meaning that 30% of patients harboring an ALK resistance mutation will test negative with our sensitivity assumption. Here, the ability of the plasma NGS to detect the presence of the original ALK rearrangement will be used as a quality control. Patients without a secondary ALK resistance mutation by plasma NGS but with a detected ALK rearrangement will be considered a true negative. Those without an ALK rearrangement identified by plasma NGS assay will be considered unevaluable for the primary purposes of the present study even if an ALK resistance mutation is identified. Additionally, plasma NGS can provide information from a wide range of genes that can elucidate off target resistance mechanisms such as p53, KRAS, PI3K, IGFR or MET. That genomic information can be obtained within the same plasma test and an exploratory analysis on these genomic alterations is planned.

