12 STATISTICAL CONSIDERATIONS

12.1 STUDY DESIGN & ENDPOINTS

A total of 300 subjects will be enrolled. Of those, we assume approximately 53% of the subjects (n=160) will have DNA shed and detectable ALK rearrangements, and will have progressed on either alectinib or ceritinib. Of the 160 subjects, we assume 80 subjects will have progressed on alectinib and 80 subjects will have progressed on ceritinib. Table 1 below shows the expected distribution of resistance mutations among these subjects.

Table 1: Expected distribution of resistance mutations

ALK mutation	Frequency after ceritinib	Frequency after alectinib
C1156Y	5%	0%
F1174X	15%	0%
I1171X	0%	10%
L1196M	0%	5%
G1202R	20%	30%
G1202del	5%	5%
D1203N	2%	0%
L1198F	5%	0%
C1156Y + L1198F	2%	2%
F1245C	0%	2%
No mutation	46%	46%

We will focus on two key mutational differences, F1174X and I1171X. With a type I error of 0.10, we have 99.8% power to detect the shown difference in acquiring the F1174X mutation, and 95.3% power to detect the shown difference in acquiring the I1171X mutation.

We will investigate response and time to treatment discontinuation (TTD) of those patients who have acquired an ALK mutation on their respective potential targeted therapy.

Table 2 below summarizes the maximum width of a 90% exact binomial confidence interval for response (CR+PR) to potential targeted therapy, per ALK mutation status.

Title: Study of Plasma Next Generation Sequencing for Remote Assessment, Characterization, Evaluation of Patients With ALK Drug Resistance (SPACEWALK)

Table 2: Max Width of 90% Exact Binomial Confidence Interval

ALK mutation	Total Sample Size	Number of Responses	Max Width of 90% CI
C1156Y	4	2	0.8043
F1174X	12	6	0.5093
I1171X	8	4	0.6143
L1196M	4	2	0.8043
G1202R	40	20	0.2779
G1202del	8	4	0.6143
D1203N	2	1	0.9491
L1198F	4	2	0.8043
C1156Y + L1198F	4	2	0.8043
F1245C	2	1	0.9491

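### Does the 70% assay sensitivity assumed in Section 5.3 go missing from the power calculation in Section 12.1?

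*Combined protocol and SAP*

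**What the plan says.** Section 5.3 sets the assay assumption on which the study is sized: "we will consider a conservative sensitivity of 70% for the NGS assay, meaning that 30% of patients harboring an ALK resistance mutation will test negative". It then makes detection of the original ALK rearrangement the quality control. A sample with no resistance mutation but "with a detected ALK rearrangement will be considered a true negative". A sample without a detected rearrangement "will be considered unevaluable for the primary purposes of the present study even if an ALK resistance mutation is identified".

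Section 12.1 enrolls 300 and assumes that "approximately 53% of the subjects (n=160) will have DNA shed and detectable ALK rearrangements" and will have progressed on alectinib or ceritinib, 80 on each. Its Table 1 "shows the expected distribution of resistance mutations among these subjects": F1174X 15% after ceritinib and 0% after alectinib, I1171X 0% and 10%, no mutation 46% in each group. At a type I error of 0.10 the section states "we have 99.8% power to detect the shown difference in acquiring the F1174X mutation, and 95.3% power" for I1171X. It names neither the test nor its sidedness for these comparisons; a one-sided error rate is labelled only in Table 3, for time to treatment discontinuation.

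**The concern.** Section 5.3 declares a sensitivity for the sample estimation, and the section that does the estimation never uses the figure. Table 1 looks undiscounted. It has 54% of subjects carrying a mutation in each group, close to the 56% that Section 5.2 reports from tumor specimens after a next-generation drug ("than on progression to crizotinib (56% vs 20%, respectively"), whereas 0.7 x 54% = 38% and 0.7 x 56% = 39%. The sample sizes in "Table 2: Max Width of 90% Exact Binomial Confidence Interval" are also the undiscounted Table 1 rates times 80: F1174X 0.15 x 80 = 12, I1171X 0.10 x 80 = 8, G1202R (0.20 + 0.30) x 80 = 40.

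If three in ten mutation carriers among the 160 were missed, the observable rates would be lower than those used for power. These are the only powers given for the primary objective, and the I1171X comparison would lose most. The label of true negative for rearrangement-positive, mutation-negative samples would also be open to question.

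**Working it through.** **Inputs (Section 12.1).** 80 per group; type I error 0.10; I1171X 10% v 0%; F1174X 15% v 0%; 160/300 = 53.3%. Section 5.3 supplies the 70%. The test is inferred, because none is named.

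**1. Reproduce the stated powers.** With zero carriers in the comparator group, the one-sided Fisher p-value for x carriers in the other group is C(80,x)/C(160,x).
- x = 3: (80 x 79 x 78)/(160 x 159 x 158) = 0.123, not significant.
- x = 4: (80 x 79 x 78 x 77)/(160 x 159 x 158 x 157) = 0.060, significant.

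With a comparator rate of exactly 0%, power is P(X >= 4) for X ~ Binomial(80, p): 96.5% at p = 0.10 and 99.9% at p = 0.15. Entering the 0% as 0.1%, an assumption about how the software was fed, and enumerating both groups gives 95.3% and 99.8%. Both printed figures are matched to the decimal at unreduced rates.

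The one-sided pooled normal formula gives 95.2% and 99.2%, a poorer match for F1174X. Two-sided Fisher gives 89.5-91.2% for I1171X, which does not match.

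**2. Can the 70% sit inside the 53%?** Let r be the proportion of subjects whose rearrangement is detected, c the proportion of mutation carriers detected among those, and s the share who progressed on the two drugs. Then overall sensitivity = r x c = 0.70, and evaluable subjects = 300 x r x s = 160. Taking r = 0.70 gives c = 1.00 and s = 160/210 = 76%. The documents state neither r nor s; the 76% is back-calculated.

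On this reading 30% of carriers still test negative, because their plasma carries too little tumor DNA. That agrees with Section 5.3, and with Section 10.3.1, which attributes a double-negative result to inadequate tumor DNA. The Table 1 rates then need no further reduction.

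**3. What if only part of the loss is there?** One-sided Fisher, 80 v 80; ranges run from a comparator rate of 0.1% to 0%.

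| Mutation detection among rearrangement-positive (c) | I1171X power | F1174X power |
|---|---|---|
| 100% | 95.3-96.5% | 99.8-99.9% |
| 90% | 92.1-93.7% | 99.4-99.6% |
| 80% | 87.0-89.1% | 98.5-99.0% |
| 70% | 79.4-82.0% | 96.5-97.4% |

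Using c = 0.70/r and s = 160/(300r):

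| r | c | s | I1171X power |
|---|---|---|---|
| 70% | 100% | 76% | 95.3-96.5% |
| 80% | 87.5% | 67% | 91.0-92.7% |
| 90% | 78% | 59% | 85.6-87.8% |
| 100% | 70% | 53% | 79.4-82.0% |

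Under this relation the last row needs every rearrangement to be detected, which would leave Section 12.1's condition of DNA shed and a detectable rearrangement with no effect. At c = 70% the pooled normal formula gives 87.5% for I1171X, so the floor also depends on the test.

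**The case for a change.** The best case for a change is that a declared input cannot be traced. The 53% merges DNA shedding, rearrangement detection and drug history with no breakdown, and nothing says that the 70% is part of it. Section 5.3 words the loss as one among mutation carriers, not as failure to detect the rearrangement. Putting all of it into the 53% requires every mutation to be seen whenever the rearrangement is, and Section 5.3 itself allows the two calls to disagree. At 70% detection among evaluable subjects, the chance of missing the I1171X difference rises from about 5% to about 20%.

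Part of this stands. The derivation is absent, the test is unnamed, and perfect detection in rearrangement-positive samples is optimistic. The rest is weaker:
- A 30% loss among carriers is what results when 30% of subjects shed too little DNA, so the wording in Section 5.3 is not contradicted.
- The disagreement that Section 5.3 provides for is a mutation seen without the rearrangement. Power falls in the opposite case, which neither section describes.
- The closeness of 54% to 56% is only suggestive. The 56% pools next-generation drugs in 48 patients, while Table 1 is specific to two drugs and cites no source. If Table 1 already gives plasma-detected rates, the stated powers stand on that ground too.
- The true-negative label is a classification rule for the analysis. Section 10.3.1 already has these results reported to subjects and physicians with caution.

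**Conclusion.** The concern does not call for a change. Both printed powers are correct for the printed inputs, and Sections 5.3 and 12.1 fit together if the 70% is the loss from DNA shedding and rearrangement detection that takes 300 to 160. The order of Section 5.3 favors that reading: sensitivity first, then rearrangement detection as quality control, then exclusion of failures.

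This rests on two assumptions that the documents do not confirm: a two-drug share of about 76%, and near-complete mutation detection once the rearrangement is seen. If the second is only roughly true, I1171X power is about 92-94% at 90% detection and 87-89% at 80%, and F1174X stays above 96% even at 70%. The 79-82% for I1171X is a corner case that also depends on the inferred Fisher test.

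What remains is missing detail: no breakdown of the 53% and no named test. Supplying it would alter no analysis, change no enrollment target and correct no figure shown to be wrong. A statistician can recover the test from the two printed powers, as above.
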